#### Exclusions

Patients who are enrolled on study but do not complete the first cycle and drop out due to any reason except dose limiting toxicity (DLT) or clinical progression will be excluded from analysis of efficacy endpoints. Reasons for such exclusions will be characterized such as consent withdrawn or eligibility subsequently not confirmed.

#### Endpoints

The primary endpoint will be the progression-free survival by RECIST 1.1 in evaluable patients treated with combination axitinib/pembrolizumab.

The secondary endpoints include:

- The objective response rate (ORR) is defined as the proportion of patients whose response by RECIST 1.1 is complete response (CR) or partial response (PR). The clinical benefit rate (CBR) is the proportion of patients whose response by RECIST 1.1 is complete response (CR), partial response (PR), or stable disease (SD). The time to progression (TTP) is defined as time from treatment initiation to first occurrence of progression by RECIST v1.1 or death of sarcoma patients treated with concurrent axitinib/pembrolizumab therapy. Overall survival (OS) is defined as the elapsed time from treatment initiation to death from any cause, whichever is earlier. Patients alive or those lost to follow-up will be censored at the last date of contact (or last date known to be alive).
- Adverse events, including dose-limiting toxicity and grade 3 or grade 4 serious adverse events
  - DLT includes treatment-related (possible, probably, or definite) grade 3 or higher toxicities as detailed in section 7.2. Toxicity will be reported by short name, type, grade, and attribution as per CTCAE v4.0.3.

The exploratory endpoints include:

- The quantity of CD3+ T-cells in peripheral blood and in tumor biopsies at each timepoint (baseline, cycle 3, and off-study).
- The expression category in tumor tissue (none (0%), low (<5%), intermediate (5-50%), or high (>50%) of various markers including PD-1, PD-L1, PD-L2, CTLA-4, TIM-3, LAG-3 at each timepoint (baseline, cycle 3, and off-study).
- The following T cell subsets will be studied in peripheral blood and tumor tissue: (CD4, CD8, T-reg, CTLA4, TIM3, LAG3, memory, naïve, PD-1, Ki67). For each marker, the absolute change in the marker(s) value will be calculated:
  - Cycle 3 marker value minus Baseline marker value
  - Progression marker value minus Cycle 3 marker value
  - Progression marker value minus Baseline marker value
- For each of the alternative (non-RECIST) radiological measurements we will categorize tumor response as CR/PR/SD vs PD. CT and/or MRI with dynamic contrast enhanced sequences will be collected throughout the study at every disease evaluation and analyzed using Choi criteria, MRI volumetrics, and

immune-related response criteria. PET/CT will be obtained at baseline, Cycle 3, and off-study and tumor response analyzed by PERCIST 1.0.

- The quantity of circulating tumor cells (CTCs) in peripheral blood will be measured at three timepoints: baseline, cycle 3, and off-study.
- RNA expression of a panel of angiogenesis and immune related genes performed using Nanostring Universal Immunooncology platform on tumor biopsies. RNA expression of immune related genes will be performed on banked peripheral blood samples by Simpatica Medicine. Expression profiles will be obtained at baseline and at Cycle 3 Day 1 on treatment.

T cell clonality indices of tumor biopsies and peripheral blood at baseline and on treatment at Cycle 3 Day 1.

Plasma angiogenic activity at baseline, Cycle 1 Day 8, and Cycle 3 Day 1.

### 16.3 Statistical Analysis

Baseline clinical and demographic characteristics of patients will be summarized. Categorical data will be summarized by the number and percent of patients in each category. Continuous variables will be summarized by descriptive statistics using mean, standard deviation, median, minimum and maximum.

#### Analysis for Primary Endpoint

The primary endpoint is progression-free survival (PFS) by RECIST 1.1 in evaluable patients treated with combination axitinib/pembrolizumab. PFS will be analyzed by Kaplan-Meier (KM) methods, and point estimates and 2-sided 95% confidence intervals for PFS will be reported for selected times such as 3, 6 and 12 months from treatment start using Greenwood's variance and the log-log transform method. Median PFS time, if attained, will also be reported.

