**Study treatment must be initiated within seven (7) days of enrollment.**

## 7.0 STUDY DESIGN

The study will be a single-institution, open-label, single-arm phase II study. Since the primary endpoint is survival outcome (PFS) sample size calculation is based on a single-arm survival design. We will employ early stopping rules for lack of efficacy, based on previously reported historical controls (19% PFS at 3 months) and a large database suggesting that a progression-free rate at 3 months of >40% correlates with an active drug in the second-line setting for patients with advanced sarcoma (43). Patients will be treated with twice daily dosing of axitinib alone for the first 7 days, followed by concurrent axitinib administered twice daily at 5 mg PO twice daily, plus intravenous administration of pembrolizumab every 21 days (Figure 3). Patients will be assessed every three weeks for toxicity. After the first five patients are enrolled, we will assess safety of the combination. If 2 or fewer patients exhibit DLT, we will

then proceed with inpatient titration of axitinib dosing at each cycle based on the presence or absence of predefined toxicities (Section 7.1, Table 3). Correlative studies characterizing T-cells in tumor tissue and in peripheral blood will be performed at three timepoints: 1. pre-treatment, 2. on-treatment on cycle 3 day 1, and 3. off-study. Additional exploratory imaging investigations, and assessment of circulating tumor cells are included for all patients (See Appendix F for complete description of correlative studies).

**Figure 3. Schematic diagram of the study.** The first cycle of treatment will be seven weeks, with one week of axitinib alone prior to initiation of pembrolizumab. Subsequently, six-week cycles of treatment consist of twice daily oral doses of axitinib administered continuously with intravenous (I.V.) administration of pembrolizumab on day 1 and 22. The first five evaluable patients will be considered a safety lead-in, and will not have axitinib dose escalation above 5 mg PO bid. If 2 or fewer patients in the safety lead-in develop DLT, axitinib will then be individually titrated based on toxicity beginning on cycle 2 day 1.

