## 12.2 Evaluations on Treatment

***Collection of Concomitant Medications should occur throughout trial treatment until 30-days ( $\pm 5$  days) post-treatment discontinuation.***

***The collection of Adverse Events (AEs) should occur throughout trial treatment and continue during Follow-up.*** Any SAE, or follow up to a SAE, including death due to any cause other than progression of the cancer under study that occurs to any subject from the time the consent is signed through **90 days** following end of treatment, or the initiation of new anti-cancer therapy, whichever is earlier, whether or not related to the Merck product, must be reported within 24 hours to the Sponsor and within 2 working days to Merck Global Safety. All subjects with SAEs must be followed up for outcome. (See Section 15.0 and Appendix A for details).

**Imaging studies should be done at the beginning of every odd cycle or 12 weeks (every 84 days  $\pm 7$  days) from the date of Registration/Enrollment, timed to coincide with the end of the prior treatment cycle; assessing all known sites of disease using the same type(s) of scan(s) that was/were performed at baseline.**

The appropriate axitinib dosing diary, blood pressure (BP) log monitoring forms and directions' sheet should be given to the patient before each treatment cycle (Appendix I). Afterwards, the dosing diary completed for that (previous) treatment cycle should be collected from the patient. This should be repeated for each cycle.

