12.2.14 Cycle 3, day 1 ( $\pm 3$  days)

The following assessments should be performed on Cycle 3, day 1:

- Note: Imaging Studies (PET/CT, CT and/or MRI) should be repeated prior to treatment every 12 weeks ( $\pm 7$  days) (i.e. every 84 days or subsequent odd cycle). If there are treatment delays leading to the patient being off schedule, scans should coincide with Day 1 of the next cycle as long as within 3 weeks. If delays greater than 3 weeks then scans should be continued every 12 weeks as per schedule.
- Collection/review of previous cycle's patient dosing diary
- PE
- ECOG PS
- V/S
- Weight

- CBC with differential
- CMP, Mg, Phosphate, direct bilirubin
- Coagulation factors
- TFTs
- U/A – (if protein 2+ or greater (grade 2) with no evidence of infection or contaminated sample, obtain urine microalbumin and urine creatinine clearance)
- Urine pregnancy test
- Correlative studies: Tumor biopsy – see Section 13.0
- Correlative studies: PET/CT, Peripheral blood collection – see Section 13.0
- Consideration for axitinib dose escalation; see Section 10.2; **for all subsequent cycles, if a patient is dose-escalated on day 1, they should keep BP log for the first three weeks of the cycle.**

12.2.15 Cycle 3, day 22 ( $\pm 3$  days) – CTU visit, pembrolizumab administration

The following assessments should be performed on Cycle 3, day 22:

- Dosing diary review, BP log reviewed if axitinib escalated on day 1
- CBC with differential
- CMP, Mg, Phosphate, direct bilirubin
- Urine pregnancy test
- If Axitinib dose escalated on (day 1) of this cycle:
  - 12 lead EKG (ONLY if axitinib dose escalation performed)

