Week (per Cycle)		1	2	3	4	5	6	7	1	2	3	4	5	6	1	4 F	Weeks 1 and 4 F,I,J	(EOT) ±7 days	30 days (±5 days) after EOT	Q12 Weeks (±7 days)	Q12 Weeks (±7 days)
Day (±3d per Cycle)	-28 to 0	1	8	15	22	29	36	43	1	8	15	22	29	36	1	22 F	Days 1 and 22 F				
Imaging scans (CT, MRI)	X	X D													X E		X E (Cycles 3,5,7,etc)	X A			
Correlatives: PET/CT	X														X			X			
Axitinib (oral)		X																			
Evaluate for Axitinib dose escalation									X						X		X (Day 1)				
Pembrolizumab (IV)			X			X			X			X			X	X	X (Days 1, 22)				

D Repeat Imaging scans (for C1D1) only if Screening/Baseline scans are deemed inadequate as per Radiology.

E After cycle 3, repeat imaging every 12 weeks or at every subsequent odd cycle (ie Cycle 5, 7, 9, etc.).

F If a patient is dose-escalated during the (specified) cycle they should be evaluated at least once on the Week 4 visit (beginning on Day 22) as well, or as clinically indicated.

G After Follow-up during “Survival” period, a telephone call to the patient and/or the patient’s family will be made to evaluate the patient’s status.

Cycle	Screening	1							2						3		Subsequent Cycles	Off Treatment (treatment discontinuation)	EoT Safety Evaluation	Follow-up A	Survival
		1	2	3	4	5	6	7	1	2	3	4	5	6	1	4 F					
Week (per Cycle)		1	2	3	4	5	6	7	1	2	3	4	5	6	1	4 F	Weeks 1 and 4 F,I,J	(EOT) ±7 days	30 days (±5 days) after EOT	Q12 Weeks (±7 days)	Q12 Weeks (±7 days)
Day (±3d per Cycle)	-28 to 0	1	8	15	22	29	36	43	1	8	15	22	29	36	1	22 F	Days 1 and 22 F				
Patient Dosing Diary Review			X	X	X	X	X	X	X	X	X	X	X	X	X	X	X (Days 1, 22)	X			
BP log review H		X	X	X	X	X	X	X	X H	X H	X H				X H	X H	X H				
Correlatives : Tumor biopsy	X														X			X			
Peripheral blood for correlative studies		X	X												X			X			
Conmeds		X																			
Pretreatment events	X																				
AEs		X (through 90-days following end of treatment)																			
Telephone call																					X G

H - BP logs are required during first cycle. For second and further cycles, if dose-escalated on day 1, patients should keep BP logs until day 22. If no change in dosing and three weeks of stable BP, logs are not required.

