## 14.0 MEASUREMENT OF EFFECT

### 14.1 Antitumor Effect in Solid Tumors

For the purposes of this study, patients should be re-evaluated for response every 12 weeks (84 days, ±7 days) from date of Enrollment, (while on treatment and until there is documented evidence of disease progression for those patients who come off treatment). Imaging studies should be timed to coincide with the end of the prior treatment cycle, assessing all known sites of disease using the same type(s) of scan(s) that was/were performed at baseline. Response assessments during follow-up after disease progression should follow the same frequency (every 12 weeks, ±7 days).

Response and progression will be evaluated in this study using the international criteria proposed by the revised Response Evaluation Criteria in Solid Tumors (RECIST) version 1.1 guideline(s). Changes in the largest diameter (unidimensional measurement) of the

tumor lesions and the shortest diameter in the case of malignant lymph nodes are used in the RECIST criteria.

The following general principles must be followed:

1. To assess objective response, it is necessary to estimate the overall tumor burden at baseline to which subsequent measurements will be compared. All baseline evaluations should be performed as closely as possible to the beginning of treatment and never more than four weeks before registration.
2. Measurable disease is defined by the presence of at least one measurable lesion.
3. All measurements should be recorded in metric notation by use of a ruler or calipers.
4. The same method of assessment and the same technique must be used to characterize each identified lesion at baseline and during follow-up.

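### The plan has no rule tying the first scheduled scan to the 3-month PFS landmark, so progression first seen on a permitted scan just after it is read as progression-free

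*Combined protocol and SAP*

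**What the plan says.** Section 2.1 makes the 3-month PFS rate the primary objective. Section 16.3 (Analysis for Primary Endpoint) analyses PFS by Kaplan-Meier; estimates and confidence intervals "will be reported for selected times such as 3, 6 and 12 months from treatment start". Section 14.2 runs PFS from treatment initiation to documented progression or death. The exception in Section 11.0 dates a confirmed RECIST progression to the scan that first showed it.

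The timing of the first on-treatment scan comes from several places:

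- Section 7.0 fixes the cycle lengths: "The first cycle of treatment will be seven weeks, with one week of axitinib alone prior to initiation of pembrolizumab". Later cycles last six weeks.
- Section 12.2: "Imaging studies should be done at the beginning of every odd cycle or 12 weeks", with the 12 weeks counted "from the date of Registration/Enrollment, timed to coincide with the end of the prior treatment cycle".
- Section 12.2.14 (Cycle 3, day 1, ±3 days): scans "should be repeated prior to treatment every 12 weeks", ±7 days. After a treatment delay, "scans should coincide with Day 1 of the next cycle as long as within 3 weeks".
- Section 12.7, footnote E: "After cycle 3, repeat imaging every 12 weeks or at every subsequent odd cycle".
- Section 14.1: "every 12 weeks (84 days, ±7 days) from date of Enrollment".

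Treatment must start within seven days of enrolment (end of Section 6.3). Section 16.4 sizes the study at 40 evaluable patients to reject a 3-month PFS rate of 19% in favour of 40%, using a one-sample survival test.

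**The concern.** Progression between scans is usually seen only at the next scan, so a Kaplan-Meier curve tends to drop on scan days. If the landmark falls on the first scan day, a shift of a day or two decides whether that drop lies before or after the reading point. Section 16.3 gives no day count for 3 months and no assessment window. It does not say how to classify progression on a first scan that is on schedule under the protocol but dated just past the landmark. As written, that patient is event-free at 3 months.

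The error runs one way: a late first scan can only raise the 3-month rate. The trial has one arm and is judged against a fixed historical figure, so no control arm shares the shift. The same undefined status feeds the exploratory analyses in Section 16.3 that use progression-free status at 3 months, including the gene-signature regression.

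**Working it through.** **The plan's own figure.** The hazard ratio is ln(0.40)/ln(0.19) = 0.552. With 15 months of accrual and 12 months of minimum follow-up, about 39.8 of 40 patients have events under the alternative. An exact chi-square test on the exponential mean gives 97.8% power with 39 events and 98.0% with 40, close to the stated 97.5%. The sizing therefore rests on a test over all follow-up, not on a count at 3 months.

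**Where the first scan can fall (days from treatment start).**

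- Landmark: 3 × 30.44 = 91.3.
- Cycle 3 Day 1: 49 + 42 = 91.
- With ±3 days: 88 to 94.
- With a 3-week delay: 91 + 21 = 112, before any visit window.
- Enrolment clock: 84 ± 7 days from enrolment, less a start gap of 0 to 7 days, gives 77 − 7 = 70 to 91 − 0 = 91.

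On the cycle schedule, permitted scans on days 92 to 112 are past the landmark. On the enrolment clock none is. If 3 months is read as 90 days, or as 84 (Section 12.5 treats 3 months and 12 weeks as interchangeable), even an on-time day-91 scan is late.

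**Effect per patient.** 1/40 = 2.5 points. Example: 40 patients, 32 with progression at the first scan and 8 without. If all 32 are dated day 91, Kaplan-Meier at day 91.3 reads 8/40 = 20%. If 4 of the 32 are dated day 94, it reads 12/40 = 30%.

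**Effect on the rate.** Assumptions, none of them in the documents: exponential PFS; a share q of first scans late and the rest on day 91; a share c of progressions documented off schedule on their true date. With S(t) the true curve,

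reading = 1 − [c(1 − S(91.3)) + (1 − c)(1 − q)(1 − S(91))].

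For a true 19%, S(91) = 0.19^(91/91.3) = 0.191. With q = 5% and c = 0: 1 − 0.95 × 0.809 = 23.1%.

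| True rate | q | c = 0 | c = 50% |
|---|---|---|---|
| 19% | 0 | 19.1% | 19.1% |
| 19% | 5% | 23.1% | 21.1% |
| 19% | 10% | 27.2% | 23.1% |
| 40% | 5% | 43.1% | 41.6% |
| 40% | 10% | 46.1% | 43.1% |

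**Reading if status is taken at each patient's own first scan.** The expected rate is then the average of S(scan day), whatever c is. For a true 19%:

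- All scans on day 91: 19.1%.
- All scans spread over days 84 to 90: 20.6%.
- 10% on day 112, where S = 0.19^(112/91.3) = 13.0%, and the rest on day 91: 0.9 × 19.1 + 0.1 × 13.0 = 18.5%.
- 10% on day 112 and the rest on days 84 to 90: 0.9 × 20.6 + 0.1 × 13.0 = 19.8%.

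The classification stays between 18.5% and 20.6%. It is not exactly unbiased, because it depends on where on-time scans fall.

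**The case against.** Five points deserve weight.

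- **The scan need not fall on the visit day.** Sections 12.2 and 14.1 time it to the end of the prior cycle, and Section 12.2.14 puts it before treatment. This stands: it pulls scans earlier and may keep the late share small. It does not rule out scans on days 92 to 94, or delay-shifted ones.
- **The late share is assumed.** This also stands. The 5 to 10% is illustrative.
- **The formal test is hardly touched.** Progression on a late scan is still an event in the one-sample survival test, in the 6- and 12-month estimates and in the median. A reader might infer that the false-positive rate of the trial is inflated. The documents do not support that: the plan has no pass mark based on a count at 3 months.
- **The shift is within sampling error.** At 19% with 40 patients the standard error is √(0.19 × 0.81/40) = 6.2 points, against about 2 to 4 points at 5% late. That is so, but a one-directional shift is not removed by a confidence interval.
- **The team seems to treat the first scan as the 3-month assessment.** Section 1.5 speaks of it in that way. This suggests intent, but Section 16.3 does not put it into effect.

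A reader might also infer that the two imaging clocks cannot both be met, or that their disagreement produces the late scans. Neither follows. A scan on day 84 from treatment start is day 84 to 91 from enrolment for every start gap of 0 to 7 days, which is inside 84 ± 7; and Section 12.2 joins its two clauses by an alternative. Late scans come from the plus side of the cycle visit window and from the delay clause.

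**Conclusion.** The gap is real and should be fixed. Followed as written, the plan scores progression first seen on a permitted scan after about day 91 as progression-free at 3 months. The size is 2.5 points per patient among 40. Under the stated assumptions a true 19% would read about 21 to 23% with 5% of first scans late and 23 to 27% with 10% late. It is nil if every first scan fell by day 91 and the landmark is taken as 91.3 days; it is larger if 3 months means 84 or 90 days. The effect is confined mainly to the 3-month estimate and the 3-month status used in the exploratory analyses. No changed trial conclusion is shown. How the historical 19% was dated is not stated, so part of the bias may cancel in that comparison.

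The difference in clocks is a separate and smaller matter. Sections 12.2 and 14.1 count from enrolment; the cycle schedule counts from treatment start, as PFS does. A scan late in Cycle 2 can satisfy both, but only one origin matches the endpoint.

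**What to change.** 1. Reconcile Sections 12.2, 12.2.14 and 14.1 to one first-scan clock counted from treatment start.
2. In Section 16.3, state the 3-month landmark in days and classify 3-month status by the first scheduled scan, with a window covering every permitted first-scan date, including delay-shifted ones.
3. Count as failures progression on that scan and any death or documented progression up to that scan or, where it was not done, up to the end of the same window. Use one cut-off for all event types, so that a death before a delayed scan is not treated more leniently than progression on it.
4. Keep Kaplan-Meier for 6 and 12 months and the median.
5. Add a sensitivity analysis on actual scan dates, or an interval-censored one.
6. State how the 19% was dated.

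The cost is wording in the analysis section and a clarifying line in the imaging schedule; no new scans. The 3-month estimate may come out slightly less favourable, or nearly unchanged if first scans fell by day 91. Comparability with 19% depends on item 6.

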#### Analysis for Secondary Endpoints

Objective response (CR or PR) and best response (CR, PR, or SD) by RECIST 1.1 to axitinib/pembrolizumab combination therapy will be tabulated, summarized and reported with 95% confidence intervals. Overall survival will be analyzed by Kaplan-Meier (KM) curves with standard error according to Greenwood's variance and the log-log transform method. Median OS will be reported if attained.

Toxicity will be summarized by reporting the number of patients treated, the number who experience DLT, SAEs and grade 3 or higher AE, the proportion of patients treated at various axitinib dose titration levels, the number of patients who discontinue therapy, and the reasons for discontinuation. Comprehensive safety data on all grade 3 and 4 toxicities will be tabulated by type, grade, duration, attribution to treatment, and dose level received.

### Analysis for Exploratory Endpoints

Although a large number of factors are being tested, we will not be making adjustments for multiple testing because these analyses are exploratory and hypothesis-generating. Findings will be validated in future larger studies.

Tumor infiltrating T-cells will be quantified by immunohistochemistry using a semiquantitative scoring system as detailed in Appendix F, Section C. We will test for association of clinical benefit status (CR/PR/SD vs PD) vs. T-cell quantity using a Wilcoxon rank sum test. We will test for association with progression-free status at 3 months (progression vs. no progression) vs. T-cell quantity using Wilcoxon rank sum test.

The expression of immune markers such as PD-1, PD-L1, PD-L2, CTLA4, TIM3, and LAG3 by immunohistochemistry will be categorized as negative (0%), low (<5%), intermediate (5-50%), or high (>50%) as detailed in Appendix F, Section C. We will test for association of clinical benefit status (CR/PR/SD vs PD) and expression category using a Chi-square test. We will test for association of expression category vs. PFS using a log-rank test.

To test for the association of the absolute change of each subset (CD4+, CD8+, T-reg, CTLA4+, TIM3+, LAG3+, memory, naïve, PD-1, Ki67) by flow cytometry in blood and tumor tissue between three timepoints (Cycle 3 marker value minus Baseline marker value, Progression marker value minus Cycle 3 marker value, Progression marker value minus Baseline marker value) with clinical benefit status (CR/PR/SD vs. PD), we will use a Wilcoxon rank sum test. Absolute changes across timepoints will be graphically presented for each marker using boxplots.

To test for the association of the absolute change between three timepoints (Cycle 3 marker value minus Baseline marker value, Progression marker value minus Cycle 3 marker value, Progression marker value minus Baseline marker value) of each subset (CD4+, CD8+, T-reg, CTLA4+, TIM3+, LAG3+, memory, naïve, PD-1, Ki67) with progression-free status at 3 months (progression vs. no progression), we will use a Wilcoxon rank sum test.

We will describe the relationship between the assessment of tumor response according to RECIST 1.1 and tumor response according to alternative radiologic methods (CT-based Choi criteria, immune related response criteria, MRI volumetrics, and PERCIST 1.0) using a 2 x 2 table to estimate the concordance between the two approaches. Results will be reported with 95% confidence interval on the proportion concordant. We are not attempting to demonstrate superiority of the alternative approaches, thus we will not use McNemar's test. We simply will describe the relationships between the approaches.

To test for the association of absolute change in CTC counts at two time points (cycle 3 and off-study) compared to baseline with clinical benefit status (CR/PR/SD vs. PD), we will use a Student t-test and Wilcoxon rank sum test for a specific time point and analysis of variance (ANOVA) and Kruskal-Wallis test for comparing all two time points. Repeated measure data analysis method will be used to analyze CTC count profiles by clinical benefit status.

To test for the association of absolute change in CTC counts at two time points (cycle 3 and off-study) compared to baseline with progression-free status at 3 months (progression vs. no progression), we will use a Student t-test and Wilcoxon rank sum test for a specific time point and analysis of variance (ANOVA) and Kruskal-Wallis test for comparing all two time points. Repeated measure data analysis method will be used to analyze CTC count profiles by progression-free status at 3 months.

Developing candidate biomarkers: We will be obtaining a large number of variables and looking for associations with response. In parallel to the above analysis, we will also utilize penalized logistic regression with bootstrapping to identify variables associated with response. We will adjust for multiple testing using Bonferroni adjustment and false discovery rate (FDR) due to multiplicity.

Genetic expression analysis: All statistical analysis will be performed by Nanostring, initially blinded to patient outcomes. Gene expression data will be log base 2-transformed and normalized using housekeeping genes selected using the nSolver 2.6 package. To identify signatures, an unsupervised cluster analysis will be performed requiring >15 genes and a correlation coefficient ( $r$ ) among the genes >0.8. Genetic signature expression will be associated with the binary outcome of progression-free status at 3 months. These signatures will be analyzed using a penalized logistic regression analysis since these signatures are high-dimensional and highly correlated with each other. Although LASSO method is used in this analysis, elastic net approach may be considered as well.

